### 2.2 Secondary Outcomes:

1). Evaluate the tolerability profile of the study therapy, analyzing the side effects.  
2). Evaluate the efficacy of the treatment in terms of subjective improvement of urinary symptoms by performing IPPS and SF-36 questionnaires and evaluate the objective improvement of urinary symptoms by performing uroflowmetry before and during treatment (during follow-up visits -up at 1,3,6 and 12 months) by means of ultrasound evaluation of the post-voiding residue, comparing the patients of the 3 study groups (Arm 1, 2 and 3).

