#### 6. Sample size and statistical analysis of the data

A total of 250 patients will be recruited. The sample analysis was performed by the "GF Ingrassia" Department of Medical, Surgical Sciences and Advanced Technologies of the University of Catania. In particular, the design foresees a 1:1:1 randomization process in 3 arms. Expect a difference of at least 2 points in IPSS and Qmax and a standard deviation of 4, as described in previous studies (Morgia et al., 2014; Alcaraz et al., 2016), it is necessary to enroll 250 patients to obtain a power 90% statistic at a significance level of 0.05.

The statistical analysis of the data collected during the study, according to an intention-to-treat procedure, will be performed using statistical software such as IBM SPSS statistics version 23.0. The variables that will be collected in order to evaluate the efficacy of the therapy will be: chronological age, weight, BMI, smoking, diabetes, PSA, IPSS, Postvoiding Residual, Qmax, QMed, Voided volume, SF-36 score. A descriptive analysis of the patients included in the three arms will be performed using the appropriate frequency measures and indices of central tendency and dispersion. Considering one pair of the three arms at a time (1 vs. 2; 1 vs. 3; 2 vs. 3), the qualitative variables will be compared using the chi-squared test; the quantitative variables will be

compared using Student's t-test. The level of significance will be set at  $p < 0.05$ . For the variables that will be significant in the univariate analysis, multivariate analyzes will be performed using appropriate regression models to control for the effect of the covariates.

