#### 8. Publication Policy

The results of this study will be summarized and presented in a final report which will have the aim of drawing reliable conclusions regarding the effective efficacy of using PEAPROSTIL 600 in the treatment of benign prostatic hypertrophy. The scientific article will then be sent to a peer-reviewed journal in the sector to be published in order to disseminate the results obtained to the scientific community. The data produced in this survey will be owned by the Ospedale Maggiore della Carità, [name].

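### The three arm pairs are each tested at an unadjusted 0.05 with no testing order or exploratory label, so the secondary comparisons do not hold the stated error rate

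*Combined protocol and SAP*

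**What the plan says.** Section 2.1 makes Arm 1 (tamsulosin plus PEAPROSTIL) against Arm 3 (tamsulosin) the primary contrast. The second item of Section 2.2 repeats the same measures (IPSS, SF-36, uroflowmetry, post-void residual) and the same visits (1, 3, 6 and 12 months), this time "comparing the patients of the 3 study groups (Arm 1, 2 and 3"). That set includes Arm 1 vs Arm 3 again, so one test is both primary and secondary.

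Section 6 gives the analysis: "Considering one pair of the three arms at a time (1 vs. 2; 1 vs. 3; 2 vs. 3"). Qualitative variables go to a chi-squared test, and quantitative ones are "compared using Student's t-test". One threshold covers everything: "The level of significance will be set at" p < 0.05. Variables that reach it go on to regression models. Section 6 names no visit for these tests.

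The plan contains no overall three-arm test, no order among the pairs, no adjustment and no exploratory label. Section 7 adds preliminary analyses of the 3- and 6-month data without an error-rate rule. Section 8 says the report aims at "drawing reliable conclusions regarding the effective efficacy of using PEAPROSTIL 600 in the treatment of benign prostatic hypertrophy" and does not say which comparisons may support that conclusion.

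**The concern.** The plan separates primary from secondary in Section 2, but Section 6 removes the distinction: all three pairs get the same test at the same threshold. Arm 1 vs Arm 2 and Arm 2 vs Arm 3 are not placed after the primary contrast, and nothing says they are descriptive. Either could therefore be reported as significant when Arm 1 vs Arm 3 is not, and the plan would give a reader no basis for discounting it.

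The regression step does not help. It selects variables on the unadjusted p-value, so it follows a chance result rather than guarding against one.

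At stake is how far secondary results can support the efficacy statement foreseen in Section 8. The separate question of which measure and visit decide the primary contrast is not covered here, although the fix depends on it being settled.

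**Working it through.** **Inputs from the plan.** Section 6: three arms, 1:1:1, total 250 (about 83.3 per arm), difference 2, standard deviation 4, 90% power, level 0.05, three pairs. Section 2.2: four measures and four visits. Not given: sidedness, and correlations between measures or visits.

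**The plan's own figure.** Section 6 says "it is necessary to enroll 250 patients to obtain a power 90% statistic at a significance level of 0.05". For two means, n per arm = 2 × (1.960 + 1.282)² × 4² / 2² = 84.06, or 85 after rounding up, and 3 × 85 = 255. With 83.3 per arm the power is 89.8%. Two-sided 0.05 therefore reproduces 250 closely. One-sided 0.05 needs 69 per arm (207 in total) and does not. The calculation fits one pairwise test on one measure, and I use two-sided 0.05 throughout.

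**One measure, one visit, no true difference.** No correlation assumption is needed, because the dependence comes only from the shared arms.
- Any of three pairs: the chance that the range of three standardised arm means exceeds 1.96 × √2 = 2.77 is 12.2%, which is 12.2 / 5 = 2.4 times the stated level. Three independent tests would give 1 − 0.95³ = 14.3%.
- Arm 1 vs 2 or Arm 2 vs 3 only: 9.1% (simulated).
- One of those two significant while Arm 1 vs 3 is not: 12.2% − 5.0% = 7.2%.

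**All measures at all visits.** This reading combines Section 2.2 with the visit schedule in Section 5.4. It gives 4 × 4 × 3 = 48 tests, of which 32 lie outside Arm 1 vs 3. I simulated 16 outcomes with an assumed common correlation, three equal arms and no true difference:

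| Event | r = 0.2 | r = 0.5 | r = 0.8 |
|---|---|---|---|
| Any of 48 tests, either direction | 84% | 68% | 42% |
| Any of the 32 non-primary tests, either direction | 74% | 58% | 35% |
| Arm 1 or Arm 2 better than Arm 3 | 43% | 30% | 17% |
| Arm 2 better than Arm 3 | 27% | 19% | 10% |

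A different assumed structure (0 to 0.7 between measures, 0 to 0.9 between visits) gives 45-86% for the first row.

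**Check of the remedy, one measure and one visit.** Test Arm 1 vs 3 at 0.05. Only if it is significant, test Arm 1 vs 2 and Arm 2 vs 3, each at 0.05.
- If Arms 1 and 3 truly do not differ, every false positive requires the first test to reject wrongly, so the error is 5.0% whatever Arm 2 does.
- If Arms 1 and 3 differ, Arm 2 can equal at most one of them. At most one null hypothesis remains, so the error is at most 5%.

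For comparison, leaving Arm 1 vs 3 outside a three-arm ANOVA gate and testing the other two pairs behind the gate gives 7.5% over the three pairs under no difference. A secondary pair then passes while the primary fails in 2.5% of trials.

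**The case against.** The plan already has part of a hierarchy. Section 2.1 names the primary pair and Section 2.2 calls the rest secondary. Unadjusted secondary comparisons are often acceptable when nobody claims them as confirmatory. This stands, and it lowers the severity. It does not remove the gap, because a secondary label alone does not say what a significant result may be used for, and Section 6 gives all pairs one rule.

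The figures assume three equal treatments. Section 1 reports that alpha-blockers typically lower IPSS by about 30-40%, and Arm 2 is the only arm without one. If Arm 2 truly differs from both other arms on a measure, its two pairs are not null and only Arm 1 vs Arm 3 can give a false positive there. That also stands, so the percentages describe the no-difference case only.

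A reader might infer three stronger things that the documents do not support:
- **That a chance finding for PEAPROSTIL is likely.** The 42-84% counts either direction and any pair. Arms 1 and 2 both take PEAPROSTIL, so Arm 1 vs 2 tests the addition of tamsulosin and is not evidence for the supplement. In PEAPROSTIL's favour against tamsulosin, the range is 17-43%.
- **That every measure is tested at every visit.** Section 6 names no visit, so the 48-test count is an inference.
- **That Section 8 lets any single significant pair support an efficacy claim.** Section 8 is a general publication statement. It fails to limit the basis for the conclusion, but it does not set such a rule.

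**Conclusion.** The concern holds in limited form. As written, the pairwise tests do not keep the stated 0.05. With no true difference, the chance of at least one significant pair on one measure at one visit is 12.2% (9.1% for the two non-primary pairs), and in 7.2% of trials a non-primary pair succeeds where the primary fails. These figures need only equal arms and two-sided tests. The larger range of 42-84% rests on the inferred 48 tests and on assumed correlations, and should be quoted with both conditions. The chance of a result in PEAPROSTIL's favour against tamsulosin, 17-43% on the same conditions, is substantial, but calling it likely goes too far. Severity is minor to moderate: a change that should be made, in a part of the plan already labelled secondary.

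**What to change.** In Sections 2.2 and 6, state:

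1. Arm 1 vs Arm 3 is tested once, as the primary contrast, and is removed from the secondary set.
2. On the same measure and visit as the primary, Arm 1 vs Arm 2 and Arm 2 vs Arm 3 are each tested at two-sided 0.05, only if Arm 1 vs Arm 3 is significant.
3. All other secondary comparisons, by measure and visit, are exploratory. They are reported as estimates with 95% confidence intervals and are not used for the efficacy conclusion in Section 8.

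Item 2 requires the plan to name one primary measure and one visit. With three arms, the order then holds the error over all three pairs at 5%, without an ANOVA gate.

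The cost is wording only: no extra patients or visits, and the primary test keeps its 0.05 level and about 90% power. By contrast, Bonferroni over three pairs (0.05 / 3 = 0.0167) would need 109 per arm (327 in total), or would leave 79.8% power with 250. The downside is that if the primary fails, neither of the other pairs can be claimed as confirmatory, and some nominally significant secondary results become exploratory.

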### 2.1 Primary Outcomes:

1) Evaluate the efficacy of the treatment in terms of subjective improvement of urinary symptoms by performing IPPS and SF-36 questionnaires and evaluate the objective improvement of urinary symptoms by performing uroflowmetry before and during treatment (during control visits follow-up at 1,3,6 and 12 months) by evaluation of the ultrasound post-voiding residue, comparing patients receiving combined therapy with tamsulosin+peaprostil (Arm 1) with patients receiving monotherapy with tamsulosin (Arm 3).

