#### 4.2 Inclusion criteria

- o Male patients aged 40 years or older
- o Patients with baseline IPSS questionnaire between 8 and 14
- o Patients with prostate volume  $\leq$  60 cc assessed by transrectal ultrasound (TRUS)
- o Patients who have a Qmax  $\leq$  15 ml/sec on uroflowmetry
- o Patients who show a post-voiding residue  $\leq$  120 ml on extemporaneous ultrasound
- o Patients who have signed the informed consent for participation in the study
- o Patients able to understand the conditions of the study and to participate for the full duration.

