#### 5.4 Post-treatment evaluation protocol

All the variables will be collected by a co-investigator of [name] team during check-ups at pre-established intervals of 1, 3, 6 and 12 months (T1, T2, T3 and T4 respectively) and will be reported in the specific data collection folder (CRF).

- at 1 month (T1), 3 months (T2), 6 months (T3) and 12 months (T4):
- Personal data: identification number and initials of the patient's name and surname, date of birth, telephone number and e-mail address
- Medical history: IPSS, SF-36
- Physical examination: abdominal, urological including rectal examination
- Uroflowmetry: morphological analysis of the flow curve, Qmax, Volume of urine emptied, RPM).

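### Post-void residual, one of several primary measures, gets only an unadjusted Student's t-test, which can lose power if follow-up residuals are skewed or a few are very high.

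*Combined protocol and SAP*

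**What the plan says.** Section 2.1 compares Arm 1 (tamsulosin plus PEAPROSTIL) with Arm 3 (tamsulosin) on IPSS, SF-36 and uroflowmetry, and "by evaluation of the ultrasound post-voiding residue". Residual is thus one primary measure among several.

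Section 4.2 restricts it at entry: "Patients who show a post-voiding residue" of at most "120 ml on extemporaneous ultrasound". No lower limit is set.

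Section 5.4 measures it again at 1, 3, 6 and 12 months ("Volume of urine emptied, RPM"; the abbreviations index defines RPM as the post-void residue). No upper limit, transformation or outlier rule applies to these values.

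Section 6 puts residual on its list of efficacy variables ("PSA, IPSS, Postvoiding Residual, Qmax, QMed, Voided volume, SF-36 score"). Quantitative variables are to be "compared using Student's t-test", one pair of arms at a time. Adjustment is conditional: "For the variables that will be significant in the univariate analysis, multivariate analyzes will be performed". The section names no rank-based method, normality check or transformation. Its sample-size assumptions cover IPSS and Qmax only.

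**The concern.** Residual is bounded at zero and has no ceiling once a man is enrolled. Section 1 of the protocol says that urinary retention is more frequent in men with BPH and that alpha-blockers do not stop it occurring. Both arms of the primary comparison take tamsulosin, follow-up lasts a year, and the analysis is by intention to treat. A long upper tail is therefore possible, and no rule in the plan deals with it.

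A few large readings inflate the pooled SD that the t-test divides by, so a real difference among most of the men may be missed. Because regression is run only after a significant t-test, the T0 residual, which Section 5.2 already collects, cannot help to recover it. The remaining option would be to change test after seeing the data, which would make the result on a primary measure look selected.

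**Working it through.** **The plan's own figure.** Inputs from Section 6: difference 2, SD 4, power 90%, alpha 0.05 (two-sided assumed; sidedness is not stated), allocation 1:1:1. The normal approximation is n = 2 × (1.960 + 1.282)² × (4/2)² = 84.1, so 85 per arm and 3 × 85 = 255 in all, against the stated 250. With 250/3 ≈ 83 per arm, power is 89.6%. The figure reproduces, but for IPSS and Qmax, not for residual.

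**Skew, with and without high values.** Everything about the residual distribution here is assumed. Follow-up residual is log-normal with median 30 ml; the treatment multiplies it by 0.7; T0 is cut off at 120 ml; the T0-to-follow-up correlation is 0.5 on the log scale. There are 83 men per arm, one follow-up visit and a two-sided test at 0.05. Simulated power:

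| Scenario | Log-SD | t-test | Wilcoxon | Gap (points) |
|---|---|---|---|---|
| No extremes | 0.6 | 95% | 97% | 2 |
| No extremes | 0.8 | 73% | 83% | 10 |
| No extremes | 1.0 | 49% | 64% | 15 |
| 2% per arm at 300 ml | 0.6 | 40% | 94% | 54 |
| 2% per arm at 300 ml | 0.8 | 36% | 77% | 41 |
| 2% per arm at 300 ml | 1.0 | 31% | 59% | 28 |

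Repeat runs moved single entries by up to about 5 points. In the 2% scenario at log-SD 0.8, ANCOVA on raw values gives 38% and rank ANCOVA 85%. Baseline adjustment on the raw scale therefore does not cure the problem, because the tail is in the follow-up values. Null rejection rates were 4.7 to 5.0%.

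**A different model.** Residual is normal with mean 50 and SD 30 ml, clipped at zero, with a 15 ml shift. Power of t-test vs Mann-Whitney is 88% vs 87% with no high values, 50% vs 86% with 1% of men at 300-600 ml, and 32% vs 85% with 2%.

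The 88% and 32% can be checked by hand, ignoring the clipping:
- No high values: SE = 30 × √(2/83) = 4.66 ml; 15/4.66 = 3.22; power = Φ(3.22 − 1.96) ≈ 90%.
- 2% at 300-600 ml (mean 450, variance 300²/12 = 7,500): control variance = 0.98 × 900 + 0.02 × 7,500 + 0.98 × 0.02 × 400² = 4,168. The treated arm has mean 35, so 415 replaces 400 and the variance is 4,408. Pooled SD = 65.5 and SE = 65.5 × √(2/83) = 10.2 ml. The shift is 0.98 × 15 = 14.7 ml; 14.7/10.2 ≈ 1.45; power = Φ(1.45 − 1.96) ≈ 30%.

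**Can one man create an effect?** One man at 500 ml moves an 83-man mean by 500/83 ≈ 6 ml. For one very large value M in one arm, the difference in means tends to M/n. The pooled variance tends to M²(1 − 1/n)/(2n − 2) = M²/(2n), so SE = √(M²/(2n) × 2/n) = M/n, and t tends to 1. In simulation with no true effect (log-SD 0.6) and one such man forced into one arm, p < 0.05 occurred in 4.1%, 1.6% and 0% of trials at 300, 500 and 1,000 ml.

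**Where ranks lose.** With 20% exact zeros and no high values, Wilcoxon loses about 5 to 8 points. If treatment only cuts the excess above 40 ml, by 70%, power is 36% / 50% / 58% (t-test) vs 10% / 11% / 14% (Wilcoxon) at log-SD 0.6 / 0.8 / 1.0. If it only prevents readings of 200-400 ml (8% of controls, 1% of treated), power is 52% vs 12%.

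**The case against.** The documents give no mean, SD or shape for residual. The large losses need a small share of very high readings, and no such frequency is stated. Entry is restricted to IPSS 8 to 14, prostate volume up to 60 cc and residual up to 120 ml, and both compared arms receive tamsulosin, so extremes may be rare. Without them the two tests differ little under mild skew. This stands: the t-test can hide an effect, but nothing shows that it will.

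Choosing ranks or means is also partly a choice of what to estimate. If the benefit lies among men with high residuals, the mean is the better target. This stands too, and it rules out demoting the mean to a supportive role.

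Section 6 leaves room for medians through its wording on descriptive indices. That is true for description, but it does not change the test.

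A reader might infer three stronger points, none of which the documents support:
- **One extreme man could look like a treatment effect.** The algebra and simulation above show the opposite: he pulls t towards 1.
- **The objective evidence rests on residual alone.** Section 2.1 also names uroflowmetry, and the sample size covers Qmax.
- **PSA needs the same change.** It is on the Section 6 list, but it is neither an outcome in Section 2.1 nor a follow-up measurement in Section 5.4.

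**Conclusion.** The point holds as a possible loss of power on one of several primary measures. Under the assumed log-normal model with a 30% reduction and 83 men per arm, the loss is about 2 to 15 points from skew alone at log-SD 0.6 to 1.0. It is about 25 to 55 points if 2% of men per arm read 300 ml. With a near-normal distribution and no high values there is essentially no loss. That the t-test would use untransformed values is inferred from the plan's silence; change scores would keep the same upper tail. The 5% error rate is not at risk, and the IPSS and Qmax sample size is unaffected. This is a low-cost improvement to the plan, not the correction of a demonstrated error.

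**What to change.** In Section 6, add for post-void residual:

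*Residual in Arm 1 vs Arm 3 will be compared by rank ANCOVA adjusted for the T0 residual, whatever the univariate result. It will be reported with medians, quartiles and the Hodges-Lehmann difference with 95% CI. The T0-adjusted mean difference with 95% CI will always be reported beside it.*

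The sentence should also name the visit to which it applies. The mean-based analysis of IPSS and Qmax stays, and nothing changes for PSA.

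Cost: a few lines of text, with no new data, visits or patients; T0 and follow-up residuals are already collected and the methods are available in the named software. There is a downside. The rank analysis describes a typical shift rather than the mean in ml, and it loses a few points of power when many residuals are exactly zero. It loses far more if the benefit is confined to high residuals, with about 10 to 15% power against about 35 to 60% for means in the example above. That is why the mean difference must be reported every time.

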## 5.2 Pre-treatment assessment

All patients will undergo an accurate analysis of the following parameters (T0).

- Personal data: identification number and initials of the patient's name and surname, date of birth, telephone number and e-mail address.
- General characteristics: gender, weight, height, smoker, coffee and/or tea intake, allergies, job, sport, diabetes mellitus.
- Medical therapy in progress.
- Remote pathological history: previous surgical interventions, underlying pathologies and number of deliveries.
- Past pathological history and diagnosis: starting date and type of symptomatology
- Assessment of quality of life (QoL questionnaire).
- Voiding assessment (IPSS questionnaire)
- Physical examination: abdominal, urological including rectal examination.
- Uroflowmetry (morphology of the curve, Qmax, Vol, RPM-residual evaluation post urination)

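### Section 6 fixes no role for the T0 value: efficacy outcomes get an unadjusted t-test, and regression adjustment depends on univariate significance

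*Combined protocol and SAP*

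**What the plan says.** Section 6 (Sample size and statistical analysis of the data) lists the variables to be analysed, including "PSA, IPSS, Postvoiding Residual, Qmax, QMed, Voided volume, SF-36 score". The arms are compared pair by pair ("Considering one pair of the three arms at a time (1 vs. 2; 1 vs. 3; 2 vs. 3"), and quantitative variables are to be "compared using Student's t-test". The only reference to adjustment is the next step: "For the variables that will be significant in the univariate analysis, multivariate analyzes will be performed using appropriate regression models", with the aim of controlling for covariates that are not listed. Section 6 does not mention T0, baseline or change from baseline.

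The baseline data exist. Section 5.2 (Pre-treatment assessment) includes at T0 "Voiding assessment (IPSS questionnaire") and uroflowmetry with Qmax, volume and post-void residual. Section 5.4 repeats these at 1, 3, 6 and 12 months. Three of the four are also entry criteria in Section 4.2: "Patients with baseline IPSS questionnaire between 8 and 14", a Qmax limit of "15 ml/sec on uroflowmetry", and a limit on residual ("Patients who show a post-voiding residue"). Their T0 values should therefore be nearly complete.

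Section 2.1 describes the primary outcome as improvement, with uroflowmetry both before and during treatment. Section 6 does not turn this into a change score or a baseline-adjusted difference.

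**The concern.** The word for what must be significant, variables, has two readings. If it means outcomes, an adjusted estimate exists only for outcomes whose t-test reached p < 0.05. If it means covariates, the covariates are picked by p-value instead of being named beforehand. Under both readings the data decide whether and how adjustment is done.

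The plan also leaves open whether the t-test is run on the follow-up value or on the change from T0. An analyst could use either, or reach an adjusted model by the regression step, and still comply with Section 6. These analyses have different power, and the T0 value is a covariate that is already paid for.

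**Working it through.** **Inputs.** From Section 6: 250 patients, three arms 1:1:1 (83 per arm), difference 2, SD 4, power 90%, significance level 0.05. Two-sided testing is assumed because the plan does not state it. Not in the documents, so assumed: the T0-to-follow-up correlation r (0.2, 0.3, 0.5) and the SD of the T0 values.

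**1. The plan's own figure.** n per arm = 2 × [4 × (1.960 + 1.282) / 2]² = 84.06, rounded up to 85, so 255 in total (252.2 unrounded). This is close to 250. Noncentral-t power at 83 per arm is 89.3%. The sample size is thus consistent with an unadjusted two-sample comparison.

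**2. ANCOVA against a t-test on follow-up values.** The residual SD is 4 × √(1 − r²), with 163 degrees of freedom against 164. The half-width is t × SD × √(2/83).

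| | t-test | r = 0.2 | r = 0.3 | r = 0.5 |
|---|---|---|---|---|
| SD | 4.00 | 3.92 | 3.82 | 3.46 |
| Power | 89.3% | 90.5% | 91.9% | 95.9% |
| 95% CI half-width | 1.23 | 1.20 | 1.17 | 1.06 |
| Per arm for 90% power | 86 | 82 | 78 | 65 |

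**3. ANCOVA against a t-test on changes.** With T0 SD s, the SD of change is √(16 + s² − 8rs). For IPSS, scores spread evenly over 8 to 14 give s = 2. For Qmax, the entry limit is at most 15 ml/sec and no lower limit is given; even spread over 7 to 15 gives s = 8/√12 = 2.31, and over 5 to 15 gives s = 10/√12 = 2.89.

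| Change-score power (ANCOVA gain in points) | r = 0.2 | r = 0.3 | r = 0.5 |
|---|---|---|---|
| IPSS, s = 2 | 87.8% (2.7) | 90.7% (1.1) | 95.9% (0) |
| Qmax, s = 2.31 | 86.2% (4.2) | 89.7% (2.2) | 95.8% (0.1) |
| Qmax, s = 2.89 | 82.2% (8.2) | 86.7% (5.2) | 94.8% (1.1) |

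**4. If the planned SD of 4 is already the SD of change.** Section 6 does not say. With s = 2 and regression slope b, the residual variance is 16 − (b − 1)² × 4. The change-score t-test has 89.3% power; ANCOVA has 92.8%, 91.1% and 89.9% at b = 0.3, 0.5 and 0.7.

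**5. The significance condition, if it applies to outcomes.** In 40,000 simulated trials per r, with a true difference of 2 and the t-test on follow-up values, the mean adjusted estimate among trials that passed was 2.12, 2.12 and 2.10 at r = 0.2, 0.3 and 0.5, about 5–6% too large. Over all trials both the adjusted and unadjusted means were 2.00. In 1.9%, 3.6% and 7.1% of trials the t-test missed significance and an ANCOVA with p < 0.05 would never have been computed.

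No figure is given for the covariate reading, since no candidate covariates or effects are stated, nor for residual and voided volume, since the plan gives no SD for them.

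**The case against.** The strongest case is that this prefers one valid method over another. The t-test is unbiased under randomisation, its overall type I error is 5%, and it is computed for every outcome, so the condition touches only a follow-on analysis. All of that stands.

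The size of the gain is also uncertain. For IPSS, r = 0.5 with a T0 SD of 2 and follow-up SD of 4 implies a slope of 0.5 × 4/2 = 1. ANCOVA then equals the change-score analysis and gains nothing over it. The narrow entry range tends to lower r, so the lower rows are the safer guide for IPSS. The Qmax gains of 4 to 8 points need a change-score t-test, r = 0.2 and an assumed lower limit.

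The simulation result needs context too. Selecting on significance inflates the unadjusted estimate in the same trials about as much (about 2.13), so the inflation is not peculiar to adjustment. The reverse discordance, a significant t-test with a non-significant ANCOVA, occurs in roughly 1% of trials, which leaves a net difference of about 1 point at r = 0.2.

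Finally, Section 2.1 speaks of measurement before and during treatment, which hints at a comparison with T0. But Section 6 never converts that into an analysis, so the choice stays open. The unnamed covariates might include T0, but a step reached only through a significance screen is not a pre-specified role. These points limit the emphasis; they do not remove the defect.

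**Conclusion.** The concern holds, as a change that should be made and not as a fatal flaw. The case rests mainly on pre-specification, which does not depend on r: Section 6 does not say how T0 enters, and the only adjustment it allows is data-dependent under either reading.

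The precision gain is small to moderate. Against follow-up values it is about 1 to 7 points of power for r from 0.2 to 0.5. Against change scores it is 0 to 3 points for IPSS and about 0 to 8 for Qmax. These figures rest on assumed r, assumed T0 spreads and, except in step 4, on reading the SD of 4 as that of the follow-up value. With that reading, ANCOVA matched or beat both kinds of t-test in every scenario examined, so there is little reason to leave the choice open.

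**What to change.** In Section 6, keep the three pairwise comparisons, the chi-squared clause, and the t-test for quantitative variables that are not efficacy outcomes (age, weight, BMI). Replace the t-test clause for efficacy outcomes and the conditional regression sentence with text such as:

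*For each pair of arms, each quantitative efficacy outcome measured at T0 (IPSS, Qmax, post-void residual, voided volume) is compared at each visit analysed by a linear model (ANCOVA) with arm and the T0 value of that outcome, fitted whatever the unadjusted p-value. The estimate, 95% CI and p-value are reported. Unadjusted t-tests are supportive. Any further covariates are named in advance and not chosen by univariate significance.*

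Add one line stating how a missing T0 value is handled; this should be rare for IPSS, Qmax and residual because they determine eligibility. SF-36, QMed and PSA are not listed by name at T0 in Section 5.2, which mentions only a QoL questionnaire. They keep the unadjusted comparison unless a T0 measurement is added. This wording does not settle which visit or outcome is primary.

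The cost is one clause, one sentence and the missing-value rule, with a little more analysis work. The SPSS software named in Section 6 fits the model, and no new data, visits or patients are needed for the four outcomes.
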